### **Method**

#### *Sample*

The study population consisted of patients aged 18 or older who were not yet enrolled in myGeisinger, who had an email address on file, for whom a lab or test was ordered within 30 days prior to the email date, and whose lab or test result was released to myGeisinger the day before the email date. Patients who had declined enrollment in myGeisinger were excluded from the study.

Based on the above criteria, N = 5,012 patients were randomized to a study condition and sent an email between May 18, 2020 and June 1, 2020 (15 days). Patients who had multiple lab/test results in this period were only randomized to a study condition once, upon their first qualifying result, and did not receive more than one email. Electronic Health Records (EHR) for study patients were subsequently examined to evaluate portal enrollment; records for 3 patients were no longer present in the EHR, leaving a total of N = 5,009 patients for analysis. All comparisons between patients emailed and those not contacted were conducted within this total.

Within the analyzed sample, 3,340 patients were allocated to an email condition. Of these, 404 were flagged by the email delivery software as invalid email addresses and were thus not sent an email. Subsequently, an additional 186 emails bounced, leaving a total of N = 2,750 emails delivered. All comparisons between the two email conditions were conducted within this total.

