## Statistical Analysis Plan

The primary question of interest was whether a timely email improves one-week patient portal enrollment when compared with no such email. This was evaluated using a logistic regression (a generalized linear model with a binary distribution and log-link function) in an intent-to-treat design: patients who were randomized to receive an email but whose addresses were scrubbed by the email delivery software were still included in any such comparisons with the control group, so the total sample size was  $N = 5,099$ .

A secondary question of interest was whether one email version performed better than the other. This question was assessed by examining whether a patient opened the email, clicked on the registration link in the email, unsubscribed from email communications, or enrolled within the outcome timeframe (1 week). This was evaluated for all four outcome measures using a logistic regression (a generalized linear model with a binary distribution and log-link function). These analyses focused on patients' responses to the two email conditions and thus only included patients who were successfully sent the email,  $N = 2,075$ . Unsubscribe data was unexpectedly unavailable at 1-week post-intervention, so this measure was collected and analyzed at 1-month post-intervention instead.

Finally, for the primary question of interest, a secondary analysis was conducted 1 month (31 days) after the intervention.

For all tests, odds ratios (ORs) were calculated, along with 95% confidence intervals (CIs); two-tailed p-values  $< 0.05$  were used to determine statistical significance.

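### The SAP puts the email-version comparison at N = 2,075, but the protocol's own counts give 2,750 for the same analyses

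*Combined protocol and SAP*

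**What the plan says.** The Sample section of the protocol sets out the flow of patients in the email arms. It starts from the number randomized to email: "Within the analyzed sample, 3,340 patients were allocated to an email condition". The first loss comes at the address screen, where "404 were flagged by the email delivery software as invalid email addresses and were thus not sent an email". The second loss comes after sending, when "an additional 186 emails bounced, leaving a total of N = 2,750 emails delivered". The section closes by fixing the analysis set for the A/B question: "All comparisons between the two email conditions were conducted within this total".

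The second paragraph of the Statistical Analysis Plan covers that same A/B question. It names four outcomes (opening the email, clicking the registration link, unsubscribing, enrolling) and says these analyses "only included patients who were successfully sent the email, $N = 2,075".

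**The concern.** Two sections of one document define the analysis set for one comparison and give different sizes. Both cannot be right. The text is in the past tense, so each figure reads as a report of what was analysed rather than as a target.

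What is at stake depends on the cause, which the documents do not settle:

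- **Digit error in the SAP.** The analysis used 2,750 and the SAP misstates the denominator of all four A/B outcomes. Any rate later formed by dividing a true count by 2,075 would be too high.
- **2,075 patients really analysed.** Then 675 patients with a delivered email were left out after randomization with no reason given. If the omissions differed between versions, or were related to the outcomes, the version comparison could be biased. It would also be less precise.

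**Working it through.** **Inputs, all from the Sample section unless noted**

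- Allocated to an email condition: 3,340
- Invalid address, not sent: 404
- Bounced: 186
- Stated total delivered: 2,750
- Stated A/B analysis set in the Statistical Analysis Plan: 2,075

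**Step 1. Reproduce the protocol's figure.**

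Delivered = allocated − invalid − bounced = 3,340 − 404 − 186 = 2,750. This agrees exactly with the protocol.

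**Step 2. Try to reproduce the SAP's figure under other readings of which patients count as sent.**

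| Reading | Calculation | Result | Excess over 2,075 |
|---|---|---|---|
| All allocated | none removed | 3,340 | 1,265 |
| Bounces only removed | 3,340 − 186 | 3,154 | 1,079 |
| Invalid addresses only removed | 3,340 − 404 | 2,936 | 861 |
| Both removed | 3,340 − 404 − 186 | 2,750 | 675 |

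None gives 2,075. The closest is the protocol's own total, still 675 away.

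**Step 3. Look for a further exclusion.** Reaching 2,075 needs 1,265 losses from 3,340. The stated losses are 404 + 186 = 590, which leaves 1,265 − 590 = 675 unexplained. Neither section describes an exclusion after delivery. The one data problem reported is that unsubscribe data could not be had at one week. That was handled by moving the measure to one month, not by removing patients. Nor is 2,075 presented as the set for a single outcome: the SAP applies it to all four.

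**Step 4. Size.**

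- Shortfall: 675 / 2,750 = 24.5%.
- If 2,075 were the true set, standard errors would be larger by a factor of √(2,750 / 2,075) = 1.151, about 15%. This assumes the same event rates and the same split between versions.
- If a count from all 2,750 were divided by 2,075, the rate would be too high by a factor of 2,750 / 2,075 = 1.325.

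**Step 5. Compare the other head count in the same SAP section.** The protocol has 5,012 randomized, less 3 no longer in the EHR: 5,012 − 3 = 5,009, or in its words "leaving a total of N = 5,009 patients for analysis". The SAP writes "so the total sample size was $N = 5,099", which is 90 higher. So both sample sizes in the SAP disagree with the protocol, and in both cases the protocol's number is the one that reconciles.

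**The case against.** The strongest reply is that this is a misprint without consequence. The figures 2,075 and 2,750 use the same four digits, and the 5,099 against 5,009 mismatch makes two slips in one short section more plausible than 675 undisclosed exclusions. Logistic regression takes its N from the rows of the data file, so a wrong number in the text changes no odds ratio, confidence interval or p-value. The documents report no outcome counts or rates, so nothing shown has been inflated by a factor of 1.325. The question is secondary, the primary email-versus-control comparison does not use this figure, and a reader can recover the intended set from the Sample section. An error in reading the PDF cannot be wholly excluded either.

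Most of this stands as a matter of emphasis. A transposition is the likelier explanation, and the 15% and 1.325 figures are conditional. The SAP's wording about sending can also reasonably be taken to mean delivered, so the phrase is ambiguous rather than a second error.

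None of it removes the conflict. The documents cannot show that the error stopped at the text, and the second mismatch is equally a reason not to rely on the SAP's counts unchecked.

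**Conclusion.** The concern holds. The SAP's 2,075 contradicts the protocol's 2,750 for the same analyses, and only 2,750 follows from the stated counts. The gap is 675 patients, 24.5% of the delivered set, and it affects the stated denominator of all four A/B outcomes.

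This is a finding about the stated N. It does not establish that 675 patients were in fact left out. If the cause is a misprint, the estimates stand and only the reported number is wrong. If it is not, there is an unexplained post-randomization exclusion of about a quarter of the set. The conclusion rests on the protocol's three flow counts being correct; they agree with its stated total. The primary comparison is not touched by this figure.

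**What to change.** 1. Check the row count of the A/B analysis file, overall and by email version, and check the figure on the printed page of the SAP.
2. If the file holds 2,750 rows, correct the SAP to N = 2,750. It would help to say delivered, as the protocol does, since 2,936 addresses passed the validity screen (3,340 − 404) and 2,750 emails arrived.
3. If the file holds 2,075 rows, rerun the four regressions on 2,750. If any further exclusion was intended, state it and justify it, with counts by email version.
4. Reconcile 5,099 with 5,009 in the same pass.

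The cost is a row count, one figure and one phrase for this point, plus the second figure in step 4. Four regressions need rerunning only if the smaller set was actually used.
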